1.2.1.1 Clinical Pharmacology

Exposure of balovaptan increased in a greater than dose-proportional manner following single doses of 0.5 to 76 mg, whereas an approximately linear increase in exposure was observed after repeated dosing with 12 to 52 mg once daily (qd) for 14 days.

Balovaptan was rapidly absorbed with a median time to maximum observed plasma concentration (T_{max}) between 1 and 4.5 hours after administration of single doses in fasted state and between 3 and 4 hours in fed state following multiple dosing. Steady state was achieved after approximately 7 days; the mean apparent elimination half-life after the last dose (Day 14) was approximately 46 hours. Food had no relevant effect on the overall exposure of balovaptan.

In the human mass balance study (Study BP29279), an almost complete absorption of the study drug was observed within the first 72 hours following administration.

In plasma, steady state exposure to [REDACTED] M3 was similar to or slightly higher than that of balovaptan and exposure to [REDACTED] M2 was lower than that of parent. M3 and M2 qualify as major metabolites in plasma.

Mean cerebral spinal fluid (CSF)-to-plasma concentration ratios of balovaptan and M3 following 7 days of dosing of 10 and 52 mg qd balovaptan were independent of dose. The ratio was approximately 12% for balovaptan, which is comparable to the balovaptan plasma free fraction (approximately 13%), and 6% for M3, which is lower than the M3 plasma free fraction (15 to 17%) reflecting M3 being a P-gp substrate. Data regarding M2 exposure in CSF is not available at this time.

Hepatic metabolism was found to be the major pathway of elimination with the primary route of excretion via urine (approximately 53% of the material recovered, mostly composed of metabolites). A further 30% of the administered dose was recovered in feces. The majority of excretion occurred within the first 7 days.

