1. A, B, C
2. A, C, B
3. B, A, C
4. B, C, A
5. C, A, B
6. C, B, A
7. A, B, D
8. A, D, B
9. B, A, D
10. B, D, A
11. D, A, B
12. D, B, A

Dosing (Days 1-15)

Each Treatment Period will involve 15 days of dosing (Day 1 – Day 15). Subjects must fast for at least 8 hours prior to and 4 hours after dosing on study days when 24-hour Holter ECG assessments will be performed (study Days 1, 2, 14 and 15). Dosing on

study days with 24-hour Holter ECG assessment should be at approximately the same time of day \pm 1h.

Prior to dosing on Day 1 subjects will undergo pre-dose assessments as outlined in the SoA ([Appendix 1](#)). Following pre-dose assessments subjects will receive a single dose of study medication preceded by a \geq 8 hour fast the night before. Study drugs will be taken with 240 mL of water and be followed by a 4-hour post-dose fast. If subjects require more liquid to take all study drugs, additional water may be provided in aliquots of 50 mL. If additional water is provided the amount should be captured. Water provided for study drug administration will be identical on all dosing days. Identical fasting procedures from Day 1 will be followed on study Days 2, 14 and 15. No fasting will be required on other dosing days. Subjects will receive standardized low salt meals on study days when 24-hour Holter ECGs (Days 1, 2, 14 and 15), ABPM (Days -1 and 12) or TT-Doppler echocardiogram (Days -1 and 13) assessments will be performed. Meals will be given at approximately the same time on each of these study days.

Days 1 and 2: 24-hour Holter ECG Assessments

On study Days 1 and 2, of each Treatment Period, 24-hour ECG assessments will be performed. Subjects will be administered study drug following a \geq 8 hour fast and continue to be fasted for 4 hours post-dose on these days. Subject will be provided with standardized low-salt meals on these days. Subjects will undergo pre and post-dose assessments as outlined in the SoA ([Appendix 1](#)).

Day 12

On study Day 12 of each Treatment Period, ABPM assessments will be performed for each subject. On study days when ABPM assessments are performed subjects will be provided with standardized low salt meals. Subjects will undergo pre and post-dose assessments as outlined in the SoA ([Appendix 1](#)).

Day 13

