On study Day 13, of each Treatment Period, at approximately the same time of day as on Day -1, TT-Doppler echocardiogram will be performed to assess any effects of steady state balovaptan levels on cardiac parameters. Subjects will receive standardized low salt meals on this study day. In addition to TT-Doppler echocardiogram subjects will undergo pre and post-dose assessments as outlined in the SoA ([Appendix 1](#)).

Days 14 and 15- 24-hour Holter ECG Assessments

On study Days 14 and 15 of each Treatment Period, 24-hour ECG assessments will be performed. Subjects will be administered study drug following a \geq 8 hour fast and continue to be fasted for 4 hours post-dose. Subjects will be provided with standardized

low salt meals on these days. Subjects will undergo pre and post-dose assessments as outlined in the SoA ([Appendix 1](#)).

Day 16

Subjects will be discharged from the CRU on the morning of Day 16 after final assessments as described in the SoA ([Appendix 1](#)).

Washout Period:

[figure not shown]
Following each Treatment Period subjects will undergo a washout period lasting a minimum of 13 and a maximum of 20 days from the last dose of study drug.

Follow-up:

Subjects will return to the unit for a follow-up visit between 14 and 21 days after the final dose of study drug. This will include a general physical examination, 12-lead ECG, vital signs, C-SSRS, adverse event review, body weight and laboratory safety tests.

[Figure 1](#) presents an overview of the study design. A SoA is provided in [Appendix 1](#).

Figure 1 Study Schema

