3.3.1 Rationale for Balovaptan and Moxifloxacin Dose and Schedule

3.3.1.1 Balovaptan

A dose of 10 mg balovaptan has shown statistically significant changes in efficacy parameters in adult male patients with ASD (Phase 2) and is the current recommended Phase 3 dose.

Balovaptan is being developed for use in ASD, so it is expected that patients will need to take it for prolonged periods of time, likely for years or for their lifetime. Hence multiple dose testing is relevant from a clinical point of view. The multiple dose PK of balovaptan with 14 days of dosing was previously characterized in humans and was found to be time-dependent. Accumulation was observed with multiple dosing, and steady state of

balovaptan was observed after approximately 7 days of dosing and after 10 days for M3. The plasma PK time course of M2 has not been closely studied but steady state has been demonstrated after 2 weeks of once daily dosing with 10 mg balovaptan.

The primary objective of this study is to investigate the effect of balovaptan on cardiac repolarization by measuring ECGs in healthy subjects at both therapeutic and supra-therapeutic doses. To this end subjects will be dosed once daily with balovaptan for 14 days at either the projected therapeutic dose of 10 mg or a supra-therapeutic dose of 50 mg and ECG parameters monitored.

In the MAD part of study BP25694 multiple doses of 12 mg (just above the clinical dose of 10 mg) resulted in a Cmax of 99 ng/mL. In Study BP28977 co-administration of itraconazole led to a 36% increase in Cmax. In the MAD part of study BP25694 multiple doses of 52 mg qd in healthy subjects were well tolerated and resulted in a Cmax of 484 ng/mL. In light of convulsions observed in dogs, dose escalation in study BP25694 was stopped so as not to exceed a Cmax of 810 ng/mL. In conclusion, based on previous clinical experience a once-daily dose of 50 mg balovaptan for 14 days is expected to be well tolerated considering the short duration of dosing in this study.

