6.6 PHARMACOKINETIC ANALYSES

Subjects will be excluded from the PK analysis population if they significantly violate the inclusion or exclusion criteria, deviate significantly from the protocol, or if data are unavailable or incomplete. Excluded cases will be documented together with the reason for exclusion. All decisions on exclusions from the analysis will be made prior to database closure.

Pharmacokinetics are a secondary objective of this study. The specific objectives are

- To investigate the pharmacokinetics of balovaptan, M2 (as appropriate), and M3.
- To investigate the pharmacokinetics of moxifloxacin.

Individual plasma concentrations at each sampling timepoint for balovaptan, M2 (as appropriate), M3, and moxifloxacin will be presented by listings and descriptive summary statistics by treatment, including means, geometric means, ranges, standard deviations and coefficients of variation. Individual and mean concentration versus time will be plotted on linear and semi-logarithmic scales.

PK parameters will be estimated using standard non-compartmental methods. All PK parameters for balovaptan, M2 (as appropriate), and M3 will be presented by individual listings and summary statistics by treatment including means, geometric means, medians, ranges, standard deviations and coefficients of variation.

The following balovaptan, M2 (as appropriate), M3 PK parameters will be estimated:

- Cmax: Day 1 and Day 14 for Treatment A and B
- AUC0-24h: Day 1 and Day 14 for Treatment A and B
- Tmax: Day 1 and Day 14 for Treatment A and B
- Ctrough: Day 11, 12, 13, 14 for Treatment A and B
- Time to steady state for Treatment A and B

The following moxifloxacin PK parameters will be estimated:

- Cmax, AUC0-24h, and Tmax will be estimated on Days 2 (Treatment C) or 15 (Treatment D)

Additional PK analyses maybe be conducted as appropriate for balovaptan, M2 (as appropriate), M3 and moxifloxacin.

Subjects will be excluded from the PK analysis population if they significantly violate the inclusion or exclusion criteria, deviate significantly from the protocol, or if data are unavailable or incomplete. Excluded cases will be documented together with the reason for exclusion. All decisions on exclusions from the analysis will be made prior to database closure.

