**Treatment B (balovaptan supra-therapeutic dose)**

Days 1-14: A single once daily oral dose of 50 mg (5 × 10 mg tablets) of balovaptan for 14 days.

Day 2 and 15: A single oral dose of a matching placebo capsule for moxifloxacin.

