### 16.2.2 Plasma Pharmacokinetic Parameters

Plasma PK parameters for balovaptan, M2, M3, and moxifloxacin will be estimated using non-compartmental methods with WinNonlin®. The plasma PK parameters will be estimated from the concentration-time profiles, and AUCs will be calculated using linear up / log down. In estimating the PK parameters, BQL values at the beginning of the profile will be set to zero. BQL values that occur after the first quantifiable point will be considered missing. Values that are embedded between BQLs, or quantifiable values occurring after two or more BQLs, will be set to missing at the discretion of the pharmacokineticist. Actual sampling times, rather than scheduled sampling times, will be used in all computations involving sampling times. If the actual time or dose time is missing, the scheduled time may be substituted in order to calculate the PK parameter.

Parameter	Description	Analytes	Treatment: Day	SAS Programming Notes
Cmax	Maximum plasma concentration. Observed peak analyte concentration obtained directly from the experimental data without interpolation, expressed in concentration units	All	A: 1 and 14 B: 1 and 14 C: 2 D: 15	Cmax from WNL
Tmax	Time to maximum plasma concentration. First observed time to reach peak analyte concentration obtained directly from the experimental data without interpolation, expressed in time units.	All	A: 1 and 14 B: 1 and 14 C: 2 D: 15	Tmax from WNL
AUC0-24	Area under the plasma concentration-time curve from time 0 to 24 hours post-dose.  If the actual 24 hr concentration was taken at or after 24 hr post-dose then AUC0-24 will be calculated by WNL to 24 hr.  If the actual 24 hr concentration was taken before nominal 24 hr and a valid $\lambda z$ is available then the data will be extrapolated to 24 hr.  If the actual 24 hr concentration was taken before 24 hr and a valid $\lambda z$ is not available, then AUC0-24 hr will be calculated to actual time closest to 24 hr within 10% of 24 (i.e., $t > 21.6$ hr)  If the actual 24 hr concentration was not taken and the last sample was taken prior to the nominal 24 hr and a valid $\lambda z$ is not available then AUC0-24 hr	All	A: 1 and 14 B: 1 and 14 C: 2 D: 15	AUC0-24 from WNL where partial time =24, if missing for a subject then AUC at nominal time 24 hr from summary file is used for AUC0-24

	will not be calculated.			

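### SAP 16.2.2 has no rule for drug still present before the Day 1 dose, so 50 mg residue enters the 10 mg Day 1 PK summaries when Treatment A directly follows B

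*SAP*

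**What the plan says.** Protocol 6.6 lists the Day 1 parameters for both balovaptan doses, for example "AUC0-24h: Day 1 and Day 14 for Treatment A and B". SAP 16.2.2 computes Cmax, Tmax and AUC0-24 on Days 1 and 14 for balovaptan, M2 and M3 and summarises them by treatment. These are secondary endpoint 4.

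On the start of a profile, SAP 16.2.2 says: "In estimating the PK parameters, BQL values at the beginning of the profile will be set to zero". Later BQL values are treated as missing. The pharmacokineticist's discretion is limited to isolated values among BQLs or values after two or more BQLs. The PK Set in SAP 10.2 has no carry-over criterion.

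The washout in Protocol 3.1 lasts "a minimum of 13 and a maximum of 20 days from the last dose of study drug". Dosing runs through Day 15: "Each Treatment Period will involve 15 days of dosing (Day 1 – Day 15"). In Treatment B the Day 15 dose is only a capsule: "Day 2 and 15: A single oral dose of a matching placebo capsule for moxifloxacin". SAP 9.2.2 counts that placebo capsule as study drug. The last balovaptan dose is therefore on Day 14, one day before the washout clock starts.

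On kinetics, Protocol 1.2.1.1 states that "the mean apparent elimination half-life after the last dose (Day 14) was approximately 46 hours". Protocol 3.3.1.1 says that steady state of "balovaptan was observed after approximately 7 days of dosing and after 10 days for M3". No M3 half-life and no assay quantification limit are given.

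**The concern.** A residue that looks negligible against the 50 mg level is five times larger relative to 10 mg. It is larger again relative to the first 10 mg dose, because Day 1 exposure is only a fraction of steady state. M3 is more exposed than balovaptan: it reaches steady state later and, being formed from the parent, cannot clear faster than the parent in the terminal phase.

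Sequences B,A,C; C,B,A; B,A,D; and D,B,A give Treatment A directly after Treatment B. In these, any residue is counted in the Day 1 Cmax and AUC0-24 as if the 10 mg dose had produced it. The affected profiles are then averaged with clean ones, with no flag and no split. At stake is the accuracy of a named secondary endpoint: the single-dose PK of 10 mg, above all for M3.

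**Working it through.** **1. Balovaptan-free gap.**
- The washout sentence: Day 15 + 13 days = next Day 1, so Day 14 to next Day 1 = 14 days. If the 13 days end at the Day -2 check-in, the gap is 16 days.
- The timeline in Protocol 3.2: 3 × 18 + 2 × 13 = 80 and 3 × 18 + 2 × 20 = 94 days, which reproduces the stated 80 to 94 days. Each 18-day block runs from Day -2 to Day 16, so the 13 days lie between Day 16 and the next Day -2. Then Day 14 to next Day 1 is 2 + 13 + 3 = 18 days.

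The two passages differ by four days.

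**2. Hand check for balovaptan (half-life 46 h).**
- 14 days: 2^(-336/46) = 0.63% of the 50 mg level; × 5 = 3.2% of the 10 mg steady state.
- 18 days: 2^(-432/46) = 0.149%; × 5 = 0.74%.
- Day 1 as a share of steady state: 1 - 2^(-24/46) = 0.303.
- Residue relative to Day 1: 3.16% / 0.303 = 10.4% at 14 days; 0.74% / 0.303 = 2.5% at 18 days.

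**3. Superposition model.** Fourteen daily 50 mg doses, a gap of G days, then one 10 mg dose.
- Parent after a unit dose: p(t) = ka/(ka - k) × (e^(-kt) - e^(-ka·t)), with k = ln 2/46 and an assumed ka of 1 per hour.
- M3: dm/dt = k·p - km·m, with km = ln 2 / (M3's own half-life). The scale cancels.
- Residue during the new profile: r(t) = 5 × Σ f(24(G + j) + t), j = 0 to 13, with f = p or m.
- Inflation = ∫r / ∫f over 0 to 24 h.

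The M3 half-life is an assumption. The value of 33 h comes from requiring M3 at 10 days to reach the same fraction of steady state as the parent at 7 days, 1 - 2^(-168/46) = 0.92. Twelve hours is a faster alternative.

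| Gap | Balovaptan | M3, 12 h | M3, 24 h | M3, 33 h |
|---|---|---|---|---|
| 14 days | +11% | +32% | +80% | +159% |
| 16 days | +5% | +15% | +39% | +79% |
| 18 days | +2.6% | +7% | +19% | +39% |

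These are AUC0-24 figures for the affected 10 mg Day 1 profiles. For balovaptan, Cmax inflation is about the same (10.5% at 14 days, 2.5% at 18). For M3 it is about half the AUC figure.

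**4. Pooled summaries.** With roughly equal allocation, 4 of 12 sequences is one third of subjects.
- Arithmetic mean at 14 days: balovaptan 11/3 = +3.7%; M3 32/3 to 159/3 = +11% to +53%.
- Arithmetic mean at 18 days: balovaptan 2.6/3 = +0.9%; M3 7/3 to 39/3 = +2% to +13%.
- The geometric mean moves less. For example, M3 at 33 h and 14 days gives 2.59^(1/3) = 1.37, or +37% against +53%. The median would also be expected to move less.

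**5. Longest washout.** Twenty days gives a gap of 21 days (washout sentence) or 25 days (timeline). Balovaptan inflation is then 0.9% or 0.2%. M3 inflation is about 2.5% to 13.5%, or 0.6% to 3.2%, over the same 12 to 33 h range.

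**The case against.** **The 14-day gap is the shortest case.** This stands. The protocol's own duration sum points to 18 days, where the balovaptan effect is trivial and the M3 effect moderate. But the washout sentence is the operative instruction and does permit 14 days. A reader might infer that Day 1 M3 will more than double in the affected profiles. The documents do not support that as an expectation: it needs both the shortest gap and an M3 half-life near 33 h.

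**The M3 figures rest on a half-life that nobody states.** This stands too. Moving the 7 or 10 days by one day shifts the solved value to between about 24 and 43 h, so 12 to 33 h is an illustrative range and not a bound. The protocol also describes the PK as time-dependent and single-dose exposure as more than dose-proportional, so a linear model is only approximate. The size is uncertain; the upward direction does not depend on the exact value.

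**The residue would be visible anyway.** Partly right. Pre-dose is a scheduled sample, SAP 16.2.1 summarises, plots and lists concentrations, and Protocol 6.6 allows additional PK analyses. But seeing a value is not a rule for handling it, and a rule chosen after the data are seen is weaker. A BQL pre-dose value does not settle the matter either, because post-dose values still contain the residue.

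**The consequence is limited.** Correct. A reader might infer that a planned accumulation ratio or a 10 versus 50 mg Day 1 test is compromised. Neither is planned: SAP 9.4.3 says there is no formal testing, and the parameters are summarised descriptively.

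**Conclusion.** The gap is real and worth closing. As written, SAP 16.2.2 lets residual balovaptan and M3 into the Treatment A Day 1 Cmax and AUC0-24 in the four sequences where A directly follows B, and pools them unmarked. In the affected profiles AUC0-24 is inflated by about 11% (14 days) or 2.6% (18 days) for balovaptan, and by about 32% to 159% or 7% to 39% for M3.

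The balovaptan figures rest on the protocol's 46 h half-life and linearity. The M3 figures also rest on an assumed own half-life of 12 to 33 h and formation from the parent.

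The effect is confined to descriptive Day 1 PK under secondary endpoint 4. It should not be read as a threat to the primary result, which is an ECG measure at 50 mg on Day 14 and uses no Day 1 PK parameter. Nor is it a finding that the washout is too short. The washout sentence and the 80 to 94 day timeline disagree and must be reconciled.

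**What to change.** Add to SAP 16.2.2, for Day 1 of Periods 2 and 3:

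- Report each analyte's pre-dose concentration as a share of that profile's Cmax.
- Flag profiles above a pre-specified share. Five percent would serve as an example; the documents give no basis for a particular cut-off, so the sponsor should choose one before unblinding.
- Summarise Treatment A Day 1 Cmax and AUC0-24 separately for periods directly after Treatment B and for all other periods.
- Add a sensitivity summary that excludes or decay-corrects the flagged profiles. Keeping this as a sensitivity summary avoids selectively removing one group of sequences from the main table.

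Separately, reconcile the washout sentence in Protocol 3.1 with the timeline in Protocol 3.2, so that the actual balovaptan-free gap is known.

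The cost is a few lines of SAP text, one extra table split, and a smaller n in the sensitivity summary (up to about one third fewer 10 mg Day 1 profiles if all those directly after B are flagged). The pre-dose samples are already scheduled, so no new sampling is needed.

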#### 16.2.2.1 Steady State

A linear plot of the arithmetic mean trough (predose) plasma concentrations versus time will be provided for Balovaptan on days 11 through 14 to visually assess the achievement of steady state. This plot will show time in days.

In addition, a statistical evaluation of steady state will also be made by dose level using the trough plasma concentrations. All valid trough concentrations on the natural-log scale will be analyzed using an analysis of variance (ANOVA) model with study day as a fixed effect. From this model, orthogonal contrasts with 95% confidence intervals (CIs) will be formed between the adjusted mean trough concentration at each study day and the mean trough concentrations for all the following study days using Helmert contrasts. Precisely, Day 11 will be compared to Day 12 through Day 14 combined; Day 12 will be compared to Day 13 through Day 14 combined; and so on.

The following SAS PROC MIXED pseudo-code may be used:

```
proc mixed data= adpc;
  by treatment;
  class day;
  model ln(trough concentration) = day / solution;
  lsmeans day / cl alpha=.05;
  estimate "Day 11 vs Days 12 - 14" day 3 -1 -1 -1 / e cl alpha=0.05
  divisor=3;
  estimate "Day 12 vs Days 13 - 14" day 0 2 -1 -1 / e cl alpha=0.05
  divisor=2;
  estimate "Day 13 vs 14" day 0 0 1 -1 / e cl alpha=0.05 divisor=2;
run;
```

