6.7.3 By-Time Point Analysis

The statistical hypothesis to be tested for the primary assessment of QT prolongation for each dose of the balovaptan treatment is:

$$H_0: \cup \{\mu_{D(i)} - \mu_{P(i)}\} \geq 10, i = 1, 2, \dots, 7$$

$$H_1: \cap \{\mu_{D(i)} - \mu_{P(i)}\} < 10, i = 1, 2, \dots, 7$$

where $\mu_{D(i)}$ and $\mu_{P(i)}$ are the least squares (LS) mean of Δ QTcF for each dose of balovaptan and placebo at time point i on Day 14, respectively.

The “by-time point” analysis for QTcF will be based on a linear mixed-effects model with change-from-baseline QTcF (Δ QTcF) as the dependent variable; gender, period, sequence, time (categorical), treatment (balovaptan, and placebo), and time-by-treatment interaction as fixed effects; and baseline QTcF as a covariate. An unstructured covariance matrix will be specified for the repeated measures at time points for subject within treatment period. If the model with an unstructured covariance matrix fails to converge, other covariance matrices such as compound symmetry and autoregressive will be considered. If the fixed effects for period and/or sequence should prove to be nonsignificant (i.e., if the p value > 0.1), these effects may be removed from the model.

and the analysis will be repeated without those covariates. From this analysis, the LS mean and 2-sided 90 % CI will be calculated for the contrast “balovaptan versus placebo” at each dose of balovaptan and each post-dose time point on Day 1 and Day 14, separately. If the upper bound of the CI lies below 10 ms for the highest dose group of balovaptan at all seven post-dose time points (0.5, 1.25, 2.5, 4, 8, 12, and 24 hours) on Day 14 (steady state), balovaptan will be concluded not to have a significant effect on QT interval prolongation.

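### The SAP's steady-state evaluation shows trough plots for balovaptan only and names no analyte in its ANOVA, although protocol 6.6 lists time to steady state for balovaptan, M2 (as appropriate) and M3

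*SAP*

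**What the plan says.** - **Protocol 6.6** opens its list with "The following balovaptan, M2 (as appropriate), M3 PK parameters will be estimated". The last item in that list is "Time to steady state for Treatment A and B". On its face, the evaluation belongs to all three analytes at both doses, with M2 qualified.
- **SAP 16.2.2.1** plans a linear plot of mean pre-dose concentrations that "will be provided for Balovaptan on days 11 through 14 to visually assess the achievement of steady state". It adds an ANOVA of log troughs with study day as the fixed effect and Helmert contrasts of each day against the later days. Neither the text nor the pseudo-code names an analyte, and the BY statement holds treatment alone.
- **SAP Appendix 4** lists one trough figure (14.2.2.4.3), titled for balovaptan, and one steady-state table (14.2.2.3) with no analyte in its title.
- **SAP 16.2.2** lists Ctrough on Days 11 to 14 for balovaptan, M2 and M3 under Treatments A and B.
- **SAP 7.1** declares no changes from the protocol.
- **Protocol 3.3.1.1** says that steady state of "balovaptan was observed after approximately 7 days of dosing and after 10 days for M3". On the remaining metabolite it says "The plasma PK time course of M2 has not been closely studied but steady state has been demonstrated after 2 weeks of once daily dosing"; the dose in that statement is 10 mg.
- **Protocol 6.7.3** attaches the steady-state label to the primary reading: "on Day 14 (steady state), balovaptan will be concluded not to have a significant effect on QT interval prolongation".

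**The concern.** The plan names one analyte for its steady-state plot, and it is the one that prior data place at plateau earliest. M3 is slower. M2 has no stated figure at 50 mg, the dose of the primary objective. Both are described as major plasma metabolites, M3 exposure is similar to or slightly above parent (protocol 1.2.1.1), and both are candidate predictors in the concentration-QTc model (protocol 6.7.7).

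Two things could go wrong if the SAP is followed as written. Either the metabolites get no steady-state evaluation, which the protocol lists and the SAP does not say it has dropped, or troughs of different analytes enter one model and the day contrasts describe none of them. In either case the steady-state label on Day 14 would lack per-analyte support.

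**Working it through.** **1. Does the stated balovaptan figure hang together?** Protocol 1.2.1.1 says: "Steady state was achieved after approximately 7 days; the mean apparent elimination half-life after the last dose (Day 14) was approximately 46 hours". With first-order accumulation, the fraction of plateau after t hours is 1 − 2^(−t/46).

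- 7 days (168 h): 1 − 2^(−168/46) = 92.0%. The 90% level is reached at 6.4 days and the 95% level at 8.3 days. This agrees with about 7 days.
- Day 11 pre-dose (10 days, 240 h): 97.3%.
- Day 14 pre-dose (13 days, 312 h): 99.1%.
- Day 14/Day 11 trough ratio: 0.991/0.973 = 1.02.

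The Days 11 to 14 window therefore has little left to detect for the parent.

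**2. What might the same window show for the metabolites?** The documents give no metabolite half-life. The following is an illustration. It assumes a first-order approach and takes steady state to mean 90% or 95% of plateau, reached at 10 days for M3 and, as the slowest reading of the protocol's statement, at 14 days for M2. With f the chosen level and T the days to reach it, k = −ln(1 − f)/T and the fraction after d days is 1 − exp(−kd).

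| Analyte | Assumed f at T | Day 11 pre-dose (d = 10) | Day 14 pre-dose (d = 13) | Ratio |
|---|---|---|---|---|
| M3 | 90% at 10 days | 90.0% | 95.0% | 1.06 |
| M3 | 95% at 10 days | 95.0% | 98.0% | 1.03 |
| M2 | 90% at 14 days | 80.7% | 88.2% | 1.09 |
| M2 | 95% at 14 days | 88.2% | 93.8% | 1.06 |

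**3. What would the ANOVA do if all three analytes were in the data?** With equal numbers of each analyte on each day, a model with day alone returns the average of the three analyte-specific contrasts. Take the first Helmert contrast, Day 11 against the mean of Days 12 to 14, on the log scale and at the 90% setting:

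- balovaptan −0.0135 (ratio 0.987), M3 −0.0389 (0.962), M2 −0.0632 (0.939);
- pooled: (−0.0135 − 0.0389 − 0.0632)/3 = −0.0385, ratio 0.962.

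At the 95% setting the three ratios are 0.987, 0.978 and 0.957, and the pooled ratio is 0.974. The pooled figure understates the slowest analyte and overstates the parent. Differences in level between analytes also go into the residual and widen the intervals.

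**4. Comparing the two documents.** The protocol's list covers three analytes, one of them qualified. The SAP's plot covers one and its ANOVA specifies none. SAP 7.1 reports no difference. These statements cannot all be taken literally.

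**The case against.** **Balovaptan may be shorthand.** SAP 16.2.1 names parent and metabolites and then summarises under balovaptan alone, and Appendix 4 titles the concentration and parameter outputs only as balovaptan or moxifloxacin. Read strictly, that would leave M2 and M3 with no PK output at all, which the SAP does not intend. The table shells are in a separate document that is not available here. This stands as far as it goes: exclusion of M2 and M3 is certain only for the literal wording of the plot, and for the ANOVA the defect is silence. It does not settle the matter, because the Ctrough row just before this section does name all three analytes, and the shorthand reading is the one under which the code would pool them.

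**The code is only a sketch.** It is offered as optional pseudo-code and also lacks a day filter, so pooling may never happen. That is fair, and it is a reason to specify the analysis rather than a reason to leave it.

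**M2 is not unknown.** A reader might take "The plasma PK time course of M2 has not been closely studied" to mean there are no data. The same sentence reports steady state after 2 weeks at 10 mg. The gap is the time course and the 50 mg dose. The protocol's qualifier on M2 also means that leaving M2 out is not automatically a departure.

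**The primary result does not depend on this.** A reader might infer that the Day 14 QTcF comparison is undermined, or that the SAP would declare steady state from the parent alone. The documents support neither. The primary objective is the effect after 14 days of dosing, and the 6.7.3 test has no steady-state condition. The concentration-QTc model uses time-matched concentrations of each analyte. SAP 16.2.2.1 sets no criterion for declaring steady state. M2 and M3 troughs are in scope for descriptive summary, so a rise would be visible in the data. These points stand and limit the importance of the issue.

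**Conclusion.** The point holds as a mismatch between protocol and SAP and an under-specified analysis. The protocol lists time to steady state for three analytes; the SAP plots one, does not specify the analyte in its ANOVA, and declares no change.

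The practical size is small. On the stated half-life, balovaptan is at about 99% of plateau by the Day 14 pre-dose sample. On the assumptions above, M3 would be at 95% to 98%, and M2 on the slowest reading at 88% to 94%. The metabolite figures are illustrations and not document values. They also say nothing specific to 50 mg, where the documents give no M2 figure.

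What is gained is a valid evaluation for each analyte and support for the steady-state label on Day 14. The primary test and its decision rule in protocol 6.7.3 need no change. The cardiodynamic analyses are defined in a separate SAP that is not available here, so how it treats metabolite steady state is unknown.

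**What to change.** In SAP 16.2.2.1:

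1. Name the analytes: balovaptan, M2 (as appropriate) and M3.
2. Add analyte to the BY statement, so that the Helmert contrasts are run separately by analyte within each dose.
3. Produce the Days 11 to 14 trough plot for each analyte, and title Figure 14.2.2.4.3, Table 14.2.2.3 and the added outputs by analyte.
4. If a balovaptan-only evaluation is intended, state it in SAP 7.1 as a change from protocol 6.6.

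While the code is open, check one separate detail: the Day 13 versus Day 14 contrast uses coefficients 1 and −1 with a divisor of 2, which gives 0.5 and −0.5 and halves the estimated log difference.

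The cost is SAP wording and a few extra plots and tables. No new samples are needed, because the metabolite troughs are already listed. The downside is more output, and the steady-state statement may need qualifying for a metabolite.
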